Appendix 8: ASDAS

Clinical Trials number: NCT03486613

ASDAS are a composite score based on patient VAS back pain, patient VAS morning stiffness, patient VAS peripheral joint pain and/or swelling, patient VAS global health and CRP level. The ASDAS formula are:

ASDAS = 0.12*Back Pain + 0.06*Morning Stiffness + 0.11*Patient Global + 0.07*Peripheral Pain/Swelling + 0.58*Ln(CRP+1)

Back pain: assessed by the patient on a 100 mm VAS scale (range 0-10)

Morning Stiffness: assessed by the patient on a 100 mm VAS scale (range 0-10)

Patient Global: assessed by the patient on a 100 mm VAS scale (range 0-10)

Peripheral Pain/Swelling: assessed by the patient on a 100 mm VAS scale (range 0-10)

Ln: natural logarithm

CRP: C-reactive protein in mg/L

The scoring range for ASDAS are:

Very high disease activity: ASDAS > 3.5

High disease activity: ASDAS = 2.1-3.5

Moderate disease activity: ASDAS = 1.3-2.0

Remission: ASDAS < 1.3

Statistical Analysis Plan (SAP): Randomised Crossover Trial

Patient-reported outcome measures collected in DANBIO reported via a smartphone app vs a touchscreen solution in an outpatient clinic among patients with inflammatory arthritis: A randomised, crossover, agreement study

Short title: The DANBIO app versus touchscreen agreement trial

[name]^{1,2,3}, [name]^{3,4}, [name]¹, [name]^{1,5}, [name]^{6,7}, [name]⁸, [name]⁸, [name]⁹, [name]¹

Affiliations

- ¹: Department of Rheumatology, Aalborg University Hospital, Aalborg, Denmark
- ²: The DANBIO Registry, Center for Rheumatology and Spine Diseases, Centre of Head and Orthopedics, Rigshospitalet, Glostrup, Denmark.
- ³: Musculoskeletal Statistics Unit, The Parker Institute, Bispebjerg and Frederiksberg Hospital, Copenhagen, Denmark
- ⁴: Research Unit of Rheumatology, Department of Clinical Research, University of Southern Denmark, Odense University Hospital, Denmark.
- ⁵: Department of Clinical Medicine, Aalborg University, Aalborg, Denmark
- ⁶: Department of Rheumatology, Aarhus University Hospital, Aarhus, Denmark
- ⁷: Department of Clinical Medicine, Aarhus University, Aarhus, Denmark
- 8: Zitelab ApS, Copenhagen, Denmark
- ⁹: Nuffield Department of Orthopaedics, Rheumatology and Musculoskeletal Sciences, University of Oxford, Oxford, UK.

Section 1: Administrative Information

Title and trial registration

Statistical analysis plan (SAP) for the DANBIO app agreement trial entitled "Patient-reported outcome measures collected in DANBIO reported via a smartphone app vs a touchscreen solution in an outpatient clinic among patients with inflammatory arthritis: A randomised, crossover, agreement

Trial registration: Clinical Trials number: NCT03486613.

SAP version

Version 1.0

November 7th 2019

Protocol version

This document has been written based on information contained in the study protocol version 1, dated December 21st 2018.

SAP revisions

None

Roles and responsibility

LU and RC designed and wrote this SAP for "the DANBIO app versus touchscreen agreement trial" in accordance to the CONSORT statement for randomised crossover trials (1). LU and RC is responsible for analysis of the trial results according to the SAP.

[name] Student, Principal investigator [name] Professor, Senior Biostatistician, [name], PhD

Section 2: Introduction

Background and rationale

Rheumatoid arthritis (RA), psoriatic arthritis (PsA) and axial spondyloarthritis (axSpA) are three major inflammatory arthritic diseases in Rheumatology. Since the 1980's, patient-reported outcome measures (PROMs) have been used in clinical research and later also in daily clinical practice as an essential tool to evaluate the patient's perception of arthritis activity. Initially, PROMs was collected in a paper form; however, in Denmark, PROMs are more feasibly collected electronically through a touchscreen solution in the outpatient clinic since 2008 (2).

Today, due to the widespread use of smartphones it is now possible and feasible to use the participants' own device for collecting PROM data via a downloaded smartphone app. Using a smartphone app instead of the standard touchscreen solution in the outpatient clinic is anticipated to eliminate problems such as having to wait in a queue, lack of privacy, and uncomfortable position during data entering etc. Furthermore, data can be collected when and where it suits the individual patient best; thereby, possibly providing more accurate answers and minimising recall-bias.

In rheumatology, Health Assessment Questionnaire Disability Index (HAQ-DI) is among the most frequently used PROMs to asses patients with RA, PsA and axSpA (3–5); thus, it makes sense to consider HAQ-DI to be one of the essential PROMs to evaluate patients with these inflammatory arthritis diseases (3–5).

Aims

To evaluate whether electronic reporting of PROMs through a smartphone app is comparable to the standard touchscreen solution in the rheumatology outpatient clinic among patients with RA, PsA and axSpA in standard clinical care.

Hypothesis

Use of a smartphone app for registration of PROMs in rheumatology yields comparable results with the standard touchscreen solution in the outpatient clinic.

Objectives

Primary objective

To demonstrate a reasonably equivalent* self-reported disability status determined by the HAQ-DI score when using a smartphone app compared to the standard touchscreen solution among patients with inflammatory arthritis enrolled in a randomised, crossover, agreement study.

*Equivalence of HAQ-DI disability status will be concluded if the 95% confidence interval for monitoring difference is within ± 0.11 HAQ-DI score points.

Secondary objectives

To evaluate whether electronic reporting of VAS (Visual Analog Scale) pain, VAS fatigue, VAS global assessment, Patient Acceptable Symptom State (PASS), anchoring question, Bath Ankylosing Spondylitis Disease Activity Index (BASDAI) and Bath Ankylosing Spondylitis Functional Index (BASFI) through a smartphone app is reasonably comparable to the standard touchscreen solution in the rheumatology outpatient clinic among patients with inflammatory arthritis. In addition, to explore whether the electronic reporting of PROMs through a smartphone app is comparable to the standard touchscreen solution in the rheumatology outpatient clinic when stratifying by diagnosis (RA, PsA or axSpA). Additionally, to evaluate whether the participants prefer reporting PROMs electronically through the DANBIO app or the standard touchscreen solution in the rheumatology outpatient clinic.

Section 3: Study Methods

Trial design

The trial is a randomised, within-participant, crossover design including patients with RA, PsA and axSpA. In a crossover study, each participant acts as his/her own control for the questionnaire comparisons; thus, each patient answered the PROM questionnaires through the DANBIO app and the touchscreen in a randomised order at two consecutive time periods. The PROM questionnaires answered in the DANBIO app was exactly the same questionnaires as the participant answered on the touchscreen in the outpatient clinic.

PROM data registration through the touchscreen in the outpatient clinic was as usual done after the participant had logged on with his/her personal civil registration (CPR) number. Before PROM data registration through the DANBIO app, the participants had to download the DANBIO app on their smartphone. Thereafter, the patient logged on the app with his/her personal identification number (nemID) and gained access to the PROM questionnaires.

After inclusion, the participants was randomised in ratio 1:1 to:

- Group App device → Touchscreen solution (AD → TS) i.e. PROM data is reported through the DANBIO app first and after a "washout period" through the touchscreen
- Group Touchscreen solution → App device (TS → AD) i.e. PROM data is reported through
 the touchscreen first and after a "washout period" through the DANBIO app

To minimise the potential carryover (recall) effect between the two PROM registrations, it was decided that there would be a "washout period "of one day between the two registrations, whereas 2 days at the latest. We anticipated that a "washout period" of one day would be enough to avoid carryover bias i.e. the effect of questionnaire recall in the second period.

Randomisation

A computer-generated randomisation sequence was produced before any patients were enrolled, allocating the participants in permuted blocks of 2 to 4, stratified by diagnosis (i.e. RA, PsA or axSpA). The three randomisation sequences were made by the senior biostatistician with no clinical involvement in the study (RC) and entered into the electronic case report form (e-CRF) in DANBIO by the independent data manager [name] (NSK). SAS PROC PLAN was used to generate the three mutually independent randomisation schedules (3 diagnoses), SAS statistical software (version 9.4.).

Power and sample size

The Minimal Important Difference (MID)/ Minimal Clinically Important Difference (MCID) for the PROMs evaluated in this trial is listed in table 2. MID/MCID describes the effect that is considered a clinically relevant reduction in the individual PROMs.

It was decided *a priori* that a difference in PROMs between groups \leq half of the MID/MCID units would be interpreted as absence of a clinically meaningful difference (i.e. agreement) (6). Thus, for HAQ-DI the equivalence margin was set to \pm 0.11 points i.e. half of the MID/MCID of 0.22 points.

The sample size was based on the following assumptions: in a two one-sided tests analysis for additive equivalence of paired means with bounds -0.11 and 0.11 for the mean difference in HAQ-DI and a significance level of 0.05, assuming a mean difference of 0 HAQ-DI points, a common standard deviation of 0.62 HAQ-DI points (7) and correlation 0.95 (between measures), a sample size of 36 pairs (12 patients with each condition) were required to obtain a power of at least 90%.

Minimal sample size: based on the same assumptions as above a sample size of 29 pairs in total (10 patients with each condition) was required to obtain a power of at least 80%. It was decided by the steering committee for this study, that in order to at least attempt to explore equivalence margins within each disease group (i.e. RA, PsA and axSpA) separately, a sample size of 20 pairs of each disease group would be feasible; i.e. enrolling 60 patients in total (corresponding to a power of 99.2%).

Framework

Although the main objective is to explore similarity between PROM devises, the precision of the estimates will be derived from a superiority analysis framework. The objective of this crossover trial is to evaluate whether electronic reporting of HAQ-DI, VAS pain, VAS fatigue, VAS global assessment, PASS, anchoring question, BASDAI and BASFI through the DANBIO app is comparable to the standard touchscreen solution in the outpatient clinics among patients with inflammatory arthritis. Furthermore, to evaluate whether electronic reporting of PROMs through the DANBIO app is comparable to the standard touchscreen solution in the outpatient clinic stratifying by diagnosis (RA, PsA or axSpA). Thus, in the outcomes listed above we will test for equivalence.

Additionally, this study will evaluate whether the participants prefer reporting PROMs electronically through the DANBIO app or the standard touchscreen solution in the outpatient clinic. Hence, this outcome will be tested for superiority.

Statistical interim analyses and stopping guidance

No interim analyses were performed during this trial; no data analyses will be done before closure of the final SAP.

Timing of final analysis

Final analysis will be performed collectively as all outcomes are short-term outcomes.

Timing of outcome assessments

The timing of outcome assessments is illustrated below in Table 1:

Table 1: Overview of time points for PROM data registration in the DANBIO-App trial

ction	
Participant enters PROM data through the 1st device	
Washout period	
Participant enters PROM data through the 2 nd device	

Section 4: Statistical Principles

Confidence intervals and P values

Level of statistical significance and use of confidence intervals

All applicable statistical analyses will be 2-sided based on a superiority framework; i.e. all confidence intervals will be presented as 95% and two-sided (95%CI).

Rationale for any adjustment for multiplicity

All applicable statistical tests and 95% confidence intervals presented will be 2-sided. Even in equivalence trials (illustrating comparability), the selection of an appropriate statistical strategy for dealing with multiplicity (repeated statistical tests) is critical for performing reliable inferences and maximizing the probability of a chance finding. Multiplicity considerations play a central role in the assessment of competing clinical objectives; i.e. the more comparisons that are made, the more likely it is that a comparison that appears to be statistically important will be falsely so (i.e. that the PROM devises appear different or with too wide 95%CIs). In order to preserve the family wise error rate of the multiple analyses, the multiplicity of the analyses of the primary and selected secondary PROMs will be presented and interpreted using a gatekeeping procedure (8). The analysis interpretation will be performed in sequence until one of the analyses has failed to be within the prespecified equivalence margin (see Table 2 below).

Adherence and protocol deviations

Acceptable compliance to the protocol is defined as participants who complete both first and second PROM data registration within the scheduled time frame.

Pre-defined major protocol violations that might occur are:

- Not completing the first and second PROM data registration
- Not completing the second PROM data registration
- No wash out period between the first and second data registration i.e. second registration performed on day 2

Pre-defined minor protocol violations are:

Delayed second data registration i.e. PROM data registration with a washout period of > 1
 days i.e. second data registration at day 4 or later

The number (N) and percentage of patients with major and minor protocol deviations will be summarised by randomisation group with details of the type of deviation. The participants that are included in the intention-to-treat (ITT) analysis data set will be used as the denominator to calculate the percentages. No formal statistical testing will be undertaken.

Analysis populations

The analyses for the primary and secondary endpoints will be conducted according to the ITT principle; i.e. based on the full analysis set (all randomised individuals having at least the first outcome measures from period 1 collected, independent of subsequent protocol violations); analyses will based on maximum likelihood (mixed linear) models, where no explicit imputation techniques (data as observed). Statistical models with missing outcome data for an individual participant are valid under the 'Missing At Random' assumption when using a maximum likelihood approach (in which estimates and standard errors are based on the likelihood function given the observed data).

Per-protocol population analyses will be performed for the primary endpoint excluding participants having major protocol violations: i.e. the per-protocol population consist of participants who adhere to the eligibility criteria and complete the first and second PROM data registration within the scheduled time points.

Section 5: Agreement Trial Population

Screening data

The screening period started at March 23rd 2019 when an invitation became visible at the end of every RA, PsA and axSpA patient's PROM data registration on the touchscreen in the outpatient clinic. The following screening data will be registered and presented:

- Length of the screening period in which the invitation to participate in the study was visible on the touchscreen in the outpatient clinic
- Length of the recruiting period i.e. from start of enrolment to the last patient is enrolled
- Number of patients screened i.e. number of patients who answered "yes" or "no" to the invite on the touchscreen in the outpatient clinic
- Number of patients, who were interested in participation and send the participant information
 and informed consent form by e-mail but did not reply i.e. did not send the signed informed
 consent form back to the investigator
- Number of patients who signed the informed consent form
- Number of patients recruited i.e. patients who were randomised
- Number of screened patients not recruited
- Reason for non-recruitment

Eligibility

Inclusion criteria:

- Diagnosed and registered in DANBIO with RA, PsA or axSpA (more than a year)
- Currently treated and monitored at the rheumatology outpatient clinic at Aalborg University Hospital
- Have previously reported PROMs in DANBIO through the touchscreen solution at the outpatient clinic ≥ 3 times

Exclusion criteria:

- Inability to provide informed consent or unwilling to comply with the study protocol
- Diagnosis of RA, PsA or $axSpA \le 12$ months
- Does not have access to a smartphone that can download and run the DANBIO app

- Not able to understand written Danish i.e. cannot understand the Danish version of the PROM questionnaires
- Visual impairment to such a degree that the participant cannot read the questionnaire in the smartphone app/on the touchscreen with e.g. glasses

The number of ineligible patients randomised, if any, will be reported, with reasons for ineligibility. Furthermore, a CONSORT flow diagram (Outline Figure 1, presented below) will provide details on the number of screened patients who were excluded due to ineligibility.

Recruitment

Recruitment of participants began at April 24th 2019.

A CONSORT flow diagram (Outline Figure 1) will summarise the number of patients who were:

- Assessed for eligibility at screening
- Eligible at screening
- Ineligible at screening¹
- Eligible and randomised
- Eligible but not randomised¹
- Followed the randomised allocation
- Did not follow the randomised allocation¹
- Lost to follow-up¹
- Discontinued the study¹
- Randomised and included in the primary analysis
- Randomised and excluded from the primary analysis¹

Withdrawal/lost to follow-up

It is expected, that participant withdrawal of consent will be small as the two PROM data registrations are undertaken within three to four consecutive days. The level of consent withdrawal will be classified as:

- Withdraw from the trial but allow use of data collected to date
- Withdraw from the trial and withdraw consent for use of data collected to date
- Lost to follow-up

^{1:} Reasons will be provided.

The CONSORT flow diagram (Outline Figure 1) will present withdrawals with numbers, reasons for withdrawal and/or exclusion from analysis at each stage i.e. first registration and second registration. Thus, withdrawals over the course of the trial will be presented with numbers and reasons summarised by treatment arm.

Baseline patient characteristics

Baseline participant characteristics will be presented in a table (Outline Table 1, presented below). Categorical data will be summarised by numbers and percentages. Continuous data will be summarised by mean, SD and range if data are normally distributed and median, IQR and range if data are skewed. Minimum and maximum values will be presented for continuous data. Tests of statistical significance for baseline characteristics will not be performed; however, the clinical importance of any imbalance will be noted.

Section 6: Analysis

Outcome measures and definitions

 Table 2: overview of definitions of the patient-reported outcome measures in this study.

Vouishi					
variable	Disease area	Unit (range)	Aims to assess	MID/MCID	Equivalence maroin
HAQ-DI	RA/PsA/axSpA	Points (0-3)	Physical function	0.22 points	± 0 11 points
VAS pain	RA/PsA/axSpA	mm (0-100)	Pain intencity	1 01	
			I am mensity	10 mm	∓ 5 mm
VAS fatigue	RA/PsA/axSpA	mm (0-100)	Fatigue severity	10 mm	± 5 mm
VAS global health	RA/PsA/axSpA	mm (0-100)	Impact on global health	10	u.
0014			inpact on Stoom inditii	10 111111	± 2 mm
FASS	RA/PsA/axSpA	Yes/No	Acceptable symptom state	N.A. ²	± 15%points
Anchoring anestion	PA/DeA/avenA	T. constitution of			J
Torrican L G	Udevana inni	Transidon scale	Change in arthritis activity	N.A. ²	± 1 unit AND
		(much worse [-3]-much better [+3])		***************************************	± 15%noints hetter
DA \$78cm3,4	D A /Do A				Tomas councils
discour	NAVESA	Foints (0.96-9.4)	Disease activity	1.2 points	± 0.6 points
ASDAS ³	PcA1/avSnA	Dointe (0 6 25)			
	ridovni vici i	1 OIIIIS (0.0-02-)	Disease activity	1.1 points	± 0.6 points
BASDAI	ANSAG	Deinta (0.100)			
	avobu	roms (0-100)	Disease activity	10 points	± 5 points
BASFI	3xSnA	Dointel (0 100)			
	rydown	1 OIIIIS (0-100)	Physical function	10 points	± 5 points
				-	201112

1: as used in the DANBIO registry

2: not applicable

3: will be estimated using a fixed level for CRP of 6

4: will be estimated using a fixed level for tender and swollen joint count respectively 1 tender joint and 0.5 swollen joint

5: no upper limit for ASDAS

Analysis methods

This study is designed and will be carried out as a randomised, crossover, agreement study. Thus, patients will be randomly assigned to one of two groups; completing either the PROM data registration on the DANBIO app or the touchscreen solution first. The order of questionnaires will be held constant, but patients enter the sequence at different time points starting with either the "app device" or "touchscreen solution". Thus, each participant will answer the questionnaires through the DANBIO app and the touchscreen in a randomised order at two successive time periods (I or II) separated by a "washout period".

In the crossover design, each participant acts as his/her own control for the question-naire comparisons. This simple manoeuvre is attractive primarily because it increases the statistical power in superiority trials. However, crossover designs can also be associated with a number of potential problems that can invalidate the results. A specific example concerns "carryover" (i.e. the residual influence of previous questionnaire responses in the subsequent period). We will attempt to evaluate and interpret a possible carryover effect statistically from the interaction between the main effects of questionnaire (app vs. touchscreen) and time period (I vs. II). We anticipate that a "washout period" of one day will be enough to avoid carryover (i.e. recall) bias. In addition, the arthritis conditions we include in this study are considered chronic and relatively stable; thus, it is highly unlikely that effects of their concomitant medication will interfere with the objective of this study (assessed only a couple of days apart).

Another caveat to the clinical interpretation of a crossover design could be the complications of analysis and interpretation arising from the loss of participants. We expect that losses of participants from the study will be small as the two data registrations are done within three days; thus, we do not anticipate that this will be an issue. A common, and generally satisfactory, use of the 2×2 crossover design is to demonstrate the equivalence of two interventions (i.e. questionnaires) all other things being equal. We assume that an equal number of participants will not adhere to the protocoled data collection ($n_{AT} \approx n_{TA}$).

Data will be analysed using SAS Proc Mixed. The MIXED procedure fits a variety of mixed linear models. A mixed linear model is a generalization of the general linear model (GLM); the generalization being that the data are permitted to exhibit correlation (i.e., from two measures on the same participant). Repeated measures from the same individuals included maximum likelihood models, analysed using mixed models enables valid inference even with missing data from individuals having only some of their outcome measures observed (9). Having a continuous outcome as the

dependent variable (e.g. HAQ-DI), our modelling component of SAS PROC MIXED will include both fixed (period [I or II]; questionnaire [App Device or Touchscreen Solution]; rheumatic condition [RA or PsA or axSpA]) and random participant (i: 1, 2, 3,, n = 60) effects.

All analyses will be adjusted for the PROM-level at enrolment covariate i.e. the last DANBIO registration of the outcome (e.g. HAQ-DI) prior to enrolment in this trial.

Statistical interpretation of agreement

According to Piaggio et al. (10), equivalence is declared if the entire 2-sided 95%CI is included within the equivalence margin. Therefore, in this study a 2-sided 95% CI for the paired difference in each individual PROM (e.g HAQ-DI) will be derived from the mixed linear model and agreement will be declared if the 95% CI of difference between PROMs is within the prespecified equivalence range (e.g., -0.11 HAQ-DI-points to +0.11 HAQ-DI-points). These margins (see Table 2, above) are based on half of the effect that is usually considered a clinically relevant reduction in the individual PROMs. Thus, based on a superiority approach it was decided *a priori* that a 95% CI excluding differences between groups of greater than half the MID/MCID units would be interpreted as indicating the absence of a clinically meaningful difference (agreement) (6).

Missing data

In case of missing data for some of the participants, PROC MIXED handles the missing values implicitly adjusting for the missing values; unlike a GLM approach a mixed linear model uses the data for the periods where there is data and ignores the periods for which there is no data (11). Provided the data are "missing at random" (MAR), the estimates from PROC MIXED are valid (12). Imputations will not be used to replace missing data in the primary analyses, but will potentially be included in a sensitivity analysis to assess the impact/robustness of the conclusions.

Additional analyses

The following pre-specified subgroup analyses will be performed on HAQ-DI to identify potentially important contextual factors. Given the relatively small numbers of participants to be recruited and the gender predominance in both RA and AS, such pre-specified subgroup analyses is likely not adequately powered. Thus, the following potentially important subgroups will be explored by using stratified analyses, using a p < 0.10 as being potentially important:

Female sex versus male sex

- RA versus other (i.e. PsA or axSpA)
- The younger half of the trial group versus the older half (median for each diagnosis)
- Age > 65 years versus age \leq 65 years (e.g. participants with anticipated IT-experience)
- Duration of data registration > 30 minutes (i.e. longer than anticipated) versus duration of data registration ≤ 30 minutes

Harms and adverse events

This study only tests the DANBIO app against the touchscreen solution in the outpatient clinic among patients with inflammatory arthritis; thus, the trial has no influence on the patient's current or future arthritis treatment. Consequently, safety data will not be collected during the course of this trial.

Statistical software

Data will be analysed using SAS Proc Mixed. The MIXED procedure fits a variety of mixed linear models.

References

- 2. DANBIO. Om DANBIO, Baggrund og historie [Internet]. [cited 2019 Jun 25]. Available from: https://danbio-online.dk/om-danbio/baggrund
- Zochling J. Measures of symptoms and disease status in ankylosing spondylitis: Ankylosing Spondylitis Disease Activity Score (ASDAS), Ankylosing Spondylitis Quality of Life Scale (ASQOL), Bath Ankylosing Spondylitis Disease Activity Index (BASDAI), Bath Ankylosing Sp. Arthritis Care Res. 2011;63:47–58.

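### Deviation percentages use an ITT set that requires period-1 data, so membership depends on a different device in each arm: a minor flaw in descriptive reporting and in the set definition

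*Protocol*

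**What the plan says.** All of the relevant text is in the SAP.

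- **Denominator** (Section 4, end of the text on adherence and protocol deviations). Major and minor deviations are tabulated as number and percentage by randomisation group. The rule for the percentages is: "The participants that are included in the intention-to-treat (ITT) analysis data set will be used as the denominator to calculate the percentages".
- **The set itself** (Section 4, Analysis populations). The ITT or full analysis set is "all randomised individuals having at least the first outcome measures from period 1 collected, independent of subsequent protocol violations".
- **Which device is period 1** (Section 3, Trial design). The app comes first in the AD→TS arm and the touchscreen comes first in the TS→AD arm.
- **Listed non-completion violations** (Section 4, Adherence and protocol deviations). There are two, both major: "Not completing the first and second PROM data registration" and "Not completing the second PROM data registration". Acceptable compliance means completing both registrations on schedule.
- **Use of partial data** (Section 6, Missing data). The mixed model is said to use whichever periods have data. Section 6.10 of the protocol says the same and sets no period-1 condition.
- **Other reporting** (Section 5, Withdrawal/lost to follow-up, and Draft Outline Figure 1). The flow diagram gives numbers and reasons at the first and second registration by arm, with a separate box (A) for participants who do not complete the first.

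**The concern.** The trial compares two devices, so failure to complete on a device is of direct interest even though it is reported only descriptively. A denominator that requires period-1 data treats the same event differently by arm. A participant who provides no app data is removed from the app-first denominator. In the touch-first arm the same failure falls in period 2, and the participant stays in the denominator and is counted as a deviation. For touchscreen failures the roles of the arms are swapped.

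Three inconsistencies follow.

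1. The violation of completing neither registration, when no period-1 data exist, can occur only in people outside the denominator over which its percentage is taken.
2. A participant who misses the first registration but completes the second is non-compliant by the SAP's own definition, yet appears in neither the major nor the minor list.
3. That same participant has outcome data but is left out of the primary analysis set, which sits badly with a model described as using every period that has data.

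At stake are the accuracy of the by-arm deviation table and the use of the ITT label for a set conditioned on a success after randomisation.

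**Working it through.** **Inputs.** 60 participants allocated 1:1, so 30 per arm (SAP Section 3). Set definition and denominator as in SAP Section 4. The documents give no failure rate and say only that losses should be small (SAP Section 6, Analysis methods). I therefore assume k = 1, 2 or 3 participants per arm who provide no app data, and no touchscreen failures.

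**The plan's own figures.** It states none for deviations. Its power figures do reproduce. The SD of the paired difference is 0.62 × √(2 × (1 − 0.95)) = 0.196. An exact paired two one-sided tests calculation with margin 0.11, true difference 0 and 5% per side gives 80.7% for 29 pairs, 90.2% for 36 and 99.2% for 60, as stated.

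**Who stays in the denominator.** App-first: the k failures have no period-1 data, leaving 30 − k. Touch-first: the k failures have touchscreen data from period 1, so all 30 stay. The SAP does not say whether the numerator is also limited to the ITT set, so both readings are shown.

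| k per arm | App-first, numerator within ITT: 0/(30 − k) | App-first, numerator from all randomised: k/(30 − k) | Touch-first, either reading: k/30 | All randomised as denominator, each arm: k/30 |
|---|---|---|---|---|
| 1 | 0/29 = 0% | 1/29 = 3.4% | 1/30 = 3.3% | 3.3% |
| 2 | 0/28 = 0% | 2/28 = 7.1% | 2/30 = 6.7% | 6.7% |
| 3 | 0/27 = 0% | 3/27 = 11.1% | 3/30 = 10.0% | 10.0% |

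On the first reading the pooled rate is k/(60 − k) = 1.7%, 3.4% and 5.3%, against 2k/60 = 3.3%, 6.7% and 10.0% over all randomised, so about half. On the second reading the arms nearly agree, but the numerator contains people who are not in the denominator. The second reading also supposes that every app-first failure is counted as a deviation. Those who went on to complete the touchscreen match no listed violation.

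**Effect on the primary analysis.** A participant without period-1 data cannot form a pair under either set definition. With k failures per arm, 60 − 2k = 58, 56 or 54 pairs remain either way, and the same power calculation gives 99.0%, 98.8% and 98.5%. A participant with only one period informs the device difference only through comparison with other participants. On the plan's SD and correlation, before any baseline adjustment, that comparison has variance 2 × 0.62² = 0.769, against 0.196² = 0.0384 for a paired difference, which is 1/(1 − 0.95) = 20 times larger. Admitting or dropping a few such participants will barely move the estimate.

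**The case against.** The strongest reply is that nothing is hidden. The flow diagram reports first-registration non-completers by arm with reasons, and also those randomised but excluded from the primary analysis. A percentage on a different but stated denominator does not contradict it. This stands. A reader might infer that app failures vanish from the report in the app-first arm; the documents do not support that. Such participants certainly leave the denominator. They leave the percentage only if the numerator is also limited to the ITT set, which the SAP does not say.

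A reader might also infer that the rule favours the app. It does not do so systematically, because touchscreen failures are handled in mirror image. Someone who gave the first period-1 measures and then stopped also remains in the set.

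App failures may be rare. The protocol excludes people without a suitable smartphone (6.3.2), checks access by telephone (7.3), and plans reminders and technical support (6.5, 6.6). The counts above are therefore illustrative only.

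Two further replies carry less weight. The missing-data text describes how the model treats absent periods, not who enters the set; that is a fair reading, but the period-1 condition still discards data the model could use. The first listed violation might be read as failing to complete both registrations, which would cover a missed first one, but the second listed violation would then be redundant.

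**Conclusion.** The point holds as a minor flaw in descriptive reporting and in the definition of the analysis set. The set called ITT is conditioned on a post-randomisation success with a different device in each arm, one listed violation does not fit its denominator, and one form of non-completion is unlisted. With one to three app failures assumed per arm of 30, the app-first arm reports 0% against 3.3% to 10.0% if the numerator is limited to the ITT set, and 3.4% to 11.1% against 3.3% to 10.0% if it is not. The first is misleading and the second is not a proper proportion. With no failures there is no discrepancy. A reader might go further and infer that the HAQ-DI equivalence conclusion is at risk. It is not: the number of complete pairs, and hence the power, is the same under either set definition, and the effect on the estimate is negligible.

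**What to change.** Make three wording changes in SAP Section 4.

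1. Use all randomised participants, by arm, as the denominator for deviation percentages. With equal failures per arm, both arms then report k/30.
2. Define the full analysis set as all randomised participants with outcome data from at least one period, in line with the description of the mixed model.
3. Add non-completion of the first registration with completion of the second to the major violations.

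No new data are needed. The only downside is that reported non-completion may look slightly less favourable.
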